# 5.3 Treatment Duration

All patients treated with either KY1044 as single agent or in combination with atezolizumab will begin study treatment on Cycle 1 Day 1. Each cycle will consist of 21 days ( $\pm$ 3 days). The next scheduled dose (as single agent or in combination) may be delayed by up to 7 days to recover from previous Aes. If the next dose (as single agent or in combination) cannot be administered within the above mentioned 7-day delay, then the dose should be skipped. Dosing will resume at the scheduled dose or the next lower dose. Dose modifications should follow Section 5.6.

If more than one consecutive dose of KY1044 as single agent or in combination with atezolizumab has to be skipped due to study treatment-related toxicities, then the default position is that IMPs should be permanently discontinued. However, if a patient who misses more than one consecutive dose due to a study treatment-related toxicity experiences clinical benefit, and in the opinion of the Investigator it is in the patient's best interest to remain on study, then the patient may continue treatment after discussion with the Medical Monitor.

A patient may continue treatment with KY1044 as single agent or in combination with atezolizumab within this clinical study, as long as they are continuing to derive benefit from treatment, until the patient experiences unacceptable toxicity or confirmed disease progression per iRECIST. Patients will not be withdrawn from the study due to progressive disease per RECIST 1.1, unless clinically indicated.

Criteria for treatment cessation or patient withdrawal from the study are outlined in Section 8, and management of toxicities is outlined in Section 5.6.

Patients with SD, PR, unconfirmed CR, and unconfirmed progressive disease will continue treatment in additional cycles.

Patients who meet the following criteria will NOT continue treatment in additional cycles:

- Patients who experience unacceptable toxicity.
- Patients with confirmed progressive disease. These patients will enter the Safety follow-up period unless the Investigator considers it to be in the patient's best interest to remain on the study, and after discussion with the Medical Monitor.

• Patients with an unconfirmed progressive disease who show signs of clinical deterioration or toxicity. These patients will enter the Safety follow-up period, and will continue to be followed-up until confirmed progressive disease or initiation of a new treatment.

Accumulating evidence indicates that objective responses to immunotherapy follows delayed kinetics of weeks or months and can be preceded by initial apparent radiological progression or appearance of new lesions (NLs) or some enlarging lesions, while other target lesions are regressing ("mixed response") (50). It is therefore reasonable to allow for these possibilities and continue to treat the patient until progression is confirmed and found to be advancing at the next imaging assessment as per iRECIST. These considerations should be balanced by clinical judgment as to whether the patient is clinically deteriorating and unlikely to receive any benefit from continued treatment.

Such deterioration will be assessed to have occurred after a clinical event that, in the Investigator's opinion, is attributable to disease progression, is unlikely to reverse with continued study treatment and therefore indicates that the patient is not benefiting from study treatment and cannot be managed by the addition of supportive care.

The decision to continue or stop treatment should be discussed with the Medical Monitor and will be documented in the study files.

The maximum duration of the treatment period for each patient within this study may be up to 48 months. Provisions may be made for patients who are still on treatment and receiving benefit at this timepoint.

# 5.4 Dose Escalation Guidelines

## 5.4.1 Starting Dose Rationale

Doses for the Phase 1 dose escalation part with KY1044 as single agent were selected based on PK/PD modelling of pre-clinical data, target engagement in tumor tissue, efficacy in pre-clinical pharmacology studies and characterization of the safety profile of KY1044 in cynomolgus monkeys and rats. The starting dose of KY1044 for the first cohort as single agent will be a single infusion of 0.8 mg KY1044. The proposed dose range for the Phase 1 dose escalation with KY1044 as single agent is 0.8 to 240 mg (and potentially above) with dose level increases between 300% to 333% for the next higher dose. Intermediate dose levels may also be explored, depending on emerging safety and PK/PD data. This dose range was selected to ensure a safe starting dose, to facilitate assessment of safety, tolerability and anti-tumor activity over a pharmacologically relevant dose range and to provide adequate exposure to support future clinical investigation of KY1044. Provisionally, the starting dose for KY1044 in combination with atezolizumab is expected also to be 0.8 mg, unless emerging safety data and the SRC recommend to start at a lower dose level. For more detail please refer to Section 5.4.2.

# 5.4.2 Provisional Dose Levels

Table 5-2 and Table 5-3 describe the starting dose for the Phase 1 parts, and the dose levels that may be evaluated during this trial.

Dose level	KY1044 proposed dose a	Increment from previous dose	Concentration after dilution	Type of infusion material
-1 b	0.24 mg	-70%	0.048 mg/mL	10 mL syringe (PP)
1 (starting dose)	0.8 mg	Starting dose	0.08 mg/mL	10 mL syringe (PP)
2	2.4 mg	300%	0.12 mg/mL	20 mL syringe (PP)
3	8 mg	333%	0.4 mg/mL	20 mL syringe (PP)
4	24 mg	300%	0.24 mg/mL d	100 mL bag (PE or PVC)
5	80 mg	333%	0.8 mg/mL d	100 mL bag (PE or PVC)
6	240 mg c	300%	2.4 mg/mL d	100 mL bag (PE or PVC)

#### Table 5-2: Provisional Dose Levels (Phase 1 KY1044 Single Agent)

MTD=maximal tolerated dose; PD=pharmacodynamics; PE=polyethylene; PK=pharmacokinetic; PP=polypropylene; PVC=polyvinyl chloride.

a It is possible for additional and/or intermediate dose levels to be added during the study. Cohorts may be added at any dose level below the MTD to better understand safety, PK or PD. Multiple dose levels below the MTD may be evaluated simultaneously in order to obtain PK and PD data across a range of doses.

b Dose level -1 represents treatment doses for patients requiring a dose reduction from the starting dose level. No dose reduction below dose level -1 is permitted for this study

c Dose levels above 240 mg may be explored depending on emerging data

d Concentrations are approximate as there may be slight variation in the fill volume of commercially available saline IV bags. The whole contents of the bag will be delivered to ensure that the entire dose is delivered to the patient.

# Table 5-3: Provisional Dose Levels (Phase 1 KY1044 in Combination with Atezolizumab)

Dose level	KY1044 proposed dose a	Atezolizumab proposed dose
-1 b	0.24 mg	1200 mg
1 (starting dose)	0.8 mg	1200 mg
2	2.4 mg	1200 mg
3	8 mg	1200 mg
4	24 mg	1200 mg
5	80 mg	1200 mg
6	240 mg °	1200 mg

MTD=maximal tolerated dose; PD=pharmacodynamic; PK=pharmacokinetic.

a It is possible for additional and/or intermediate dose levels to be added during the study. Cohorts may be added at any dose level below the MTD in order to better understand safety, PK or PD. Multiple dose levels below the MTD may be evaluated simultaneously in order to obtain PK and PD data across a range of doses.

b Dose level -1 represents treatment doses for patients requiring a dose reduction from the starting dose level. No dose reduction below dose level -1 is permitted for this study.

c Dose levels above 240 mg maybe explored depending on emerging data

# 5.4.3 Cohort Modification

For the purposes of dose escalation decisions (Phase 1 of KY1044 as single agent or in combination with atezolizumab), each cohort will consist of three newly enrolled patients who will be treated at the specified dose level and will meet the criteria in Section 4.1.1. Should only two of these patients in the first cohort recruited to the study be considered evaluable (ie, meet the criteria described below for a patient to be considered evaluable [Section 5.4.5.1]) and neither patient has experienced a treatment-related toxicity CTCAE v5 >Grade 1, then a dose escalation decision may be made following a dose escalation meeting. If, one or both patients experience a treatment-related toxicity CTCAE v5 >Grade 1, or if the SRC decide additional information is required before making a dose escalation decision, then additional patients will be enrolled to this cohort to reach the minimum of three evaluable patients. Subsequent cohorts will have at least three evaluable patients.

# 5.4.4 Dose Escalation Procedures

The first cohort enrolled in the study will be treated with single agent KY1044 at the starting dose as specified in Table 5-2. Once this cohort has completed the DLT follow-up period (21 days) and the dose escalation decision has been determined by the SRC to escalate, the second cohort for the single agent will open for dosing. After the first two cohorts have been declared safe and tolerable, combination dosing will begin at the planned starting dose in parallel to proceeding with dose escalation of the single agent.

The combination dose escalation will proceed provided that the starting dose of the combination does not exceed the MTD of the single agent. Provisionally, the first cohort enrolled in the study will be treated with the starting dose for KY1044 at a flat dose of 0.8 mg in combination with atezolizumab (a lower dose of KY1044 may be considered for starting the combination if emerging data support this, but will not be higher than 0.8 mg for KY1044 and 1200 mg for atezolizumab).

The assessment of DLT data will be made after the third patient in a given cohort has completed the minimum DLT follow-up period (21 days) or is otherwise evaluable (see Section 5.4.5.1). The SRC will meet for the dose escalation meeting, once required data have been entered into the eCRF, cleaned and laboratory analyses have been performed.

After the dose escalation meeting, the new dose will be officially confirmed and the new cohort will be opened for dosing patients. Drug administration at the next dose level may not proceed until the Investigator receives written confirmation, indicating that the results of the previous dose level were evaluated and that it is permissible to proceed to a higher dose level. The number of cohorts explored will be dependent on the tolerability of the compound.

Dose escalation will continue until identification of the MTD and/or the RP2D, completion of all defined dose levels, or a decision that further increase of dose is not warranted.

# 5.4.5 Dose Escalation Decisions

# 5.4.5.1 Evaluable Patients

For dose escalation decisions, patients in either single agent or combination cohorts can be considered evaluable after having met the following criteria:

- Have completed a minimum of one cycle of treatment with the minimum safety evaluation (Cycle 1, 21 days) or have had a DLT within the first cycle of treatment (first 21 days)
- Have adequate drug exposure (ie, full infusion of planned doses of KY1044 and atezolizumab if appropriate)

Dose escalation decisions will occur when the cohort of at least three patients has met these criteria. If only two patients in a cohort are evaluable and neither patient has experienced a treatment-related toxicity CTCAE v5>Grade 1, dose escalation decisions may be considered (see Section 5.4.3).

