# 4.1.1 Number of Patients for Dose Escalation and Cohort Composition

The Phase 1 dose escalation parts of the study will be based on cohorts of 3 patients. More patients may be enrolled into each cohort to assure at least 3 evaluable patients for dose escalation decisions. To assess the safety profile of KY1044 it will be required that each cohort satisfies the following requirements:

• At least two patients are anti-PD-(L)1 naïve.

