### 8.3 Replacement Policy

### 8.3.1 Phase 1 Dose Escalation Parts:

Patients will not be replaced on study. However, if a patient is considered to be non-evaluable for the dose escalation, enrolment of a new patient to the current cohort will be considered if there is less than the required number of evaluable patients (see Section 5.4.5.1). Enrolment of new patients may be considered until at least the minimum number or at most the maximum number of evaluable patients is achieved within the cohort. Minimum and maximum numbers of evaluable patients per cohort are defined in Section 4.1.1.

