### Figure 9-1: mTPI-2 Decision Table

Sample size=36, Target toxicity probability=0.3, epsilon 1=0.05, epsilon 2=0.05

\* Column indicates the number of patients treated. Row indicates the number of patients with DLTs

\*  $\mathbf{E}$ : Escalate to the next higher dose;  $\mathbf{S}$ : Stay at the same dose;  $\mathbf{D}$ : De-escalate to the previous lower dose;  $\mathbf{D}$ : De-escalate to the previous lower dose and the current dose will never be used again in the trial. Two parameters e1 and e2 are set at default values (Guo. et al. 2017) of 0.05.

The mTPI-2 design is chosen for this trial because it has demonstrated superior operating characteristics when compared with standard methods, such as the 3+3 design, and is easy to implement with precalculated dose decision rules (56).

Section 9.1.2 presents comprehensive simulation results of mTPI-2 and its operating characteristics. See Appendix 4 for the detailed technical summary of the design and simulations.

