7.2.5 Dose Limiting Toxicity Evaluable Set

The DLT evaluable set will be patients who have been on study for 1 full cycle (21 days) and have received adequate treatment with KY1044 as single agent or in combination with atezolizumab (i.e. have had full infusion of planned doses of KY1044 and Atezolizumab if appropriate) or have experienced a DLT in Cycle 1. The evaluation of DLTs in Phase 1 of the study will occur in this population.

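### Protocol 5.4.5.1 has no DLT exception to its full-infusion requirement, so a patient whose Cycle 1 infusion is stopped by a DLT is literally non-evaluable, contrary to SAP 7.2.5

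*Protocol*

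**What the plan says.** Protocol 5.4.5.1 lists two criteria for a patient to be evaluable for escalation decisions. The first is completion of Cycle 1 with the minimum safety evaluation, or a DLT within its 21 days. The second, in a separate bullet, is "Have adequate drug exposure (ie, full infusion of planned doses of KY1044 and atezolizumab if appropriate"). The section then has decisions made once at least three patients have met the criteria, so both must be satisfied.

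SAP 7.2.5 uses the same elements in a different order. It asks for a full cycle with full infusion, and adds after both conditions "or have experienced a DLT in Cycle 1".

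Evaluability has operational consequences in the protocol:
- Section 5.4.4 times the DLT assessment to when the third patient has finished 21 days "or is otherwise evaluable (see Section 5.4.5.1").
- Section 4.1.1: "More patients may be enrolled into each cohort to assure at least 3 evaluable patients for dose escalation decisions".
- Section 5.4.3: "Subsequent cohorts will have at least three evaluable patients".
- Section 8.3.1: "Patients will not be replaced on study", but "if a patient is considered to be non-evaluable for the dose escalation, enrolment of a new patient to the current cohort will be considered" when a cohort has too few evaluable patients.

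The counting rule for the mTPI-2 table is stated elsewhere. Section 9.1.1 bases decisions on the Section 5.5 DLT criteria once all outcomes of a cohort are observed. The legend to Figure 9-1 reads "Column indicates the number of patients treated. Row indicates the number of patients with DLTs", and SAP Appendix 12.1 repeats it. Section 5.4.6.1 defines the MTD by the DLT rate among treated patients.

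**The concern.** A patient who has a DLT is informative however little drug was given, and should always be evaluable. By its wording, 5.4.5.1 excludes the patient whose DLT is what prevented full infusion.

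The case is foreseeable. Section 5.2.4 requires permanent discontinuation for infusion reactions above Grade 2. Section 7.1.6 makes infusion reactions of Grade 3 or above an adverse event of special interest for KY1044. Infusion reaction is not among the named Grade 3 exceptions in Table 5-4.

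In the combination arm the KY1044 infusion need not even be cut short. Section 5.2.2 leaves about one hour between KY1044 and atezolizumab, and Section 8 requires a patient who stops KY1044 for an adverse event to stop atezolizumab too. A DLT in that hour leaves the planned atezolizumab dose ungiven.

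At stake is the SRC's tally. If it were restricted to 5.4.5.1-evaluable patients, it would omit a DLT that the SAP's DLT set reports.

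**Working it through.** **1. Classify one patient under each rule.** Take a patient with a DLT during the Cycle 1 infusion, which is then stopped.
- Protocol 5.4.5.1: criterion 1 met (DLT), criterion 2 not met (infusion incomplete). Not evaluable.
- SAP 7.2.5: DLT in Cycle 1. Evaluable.
- Figure 9-1 legend and Section 5.5: a treated patient with a DLT, and Section 5.5 sets no completed-infusion condition. Counts in both row and column.

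**2. Rebuild the decision rule.** Stated inputs (Section 9.1, Appendix 4): target 0.30, e1 = e2 = 0.05, subintervals of width 0.10 on either side of 0.25–0.35. Assumed, because the documents do not state them: a Beta(1,1) prior, and exclusion of a dose when P(p > 0.30) exceeds 0.95. With x DLTs in n patients the posterior is Beta(1+x, 1+n−x). The unit probability mass of an interval (a, b) is [F(b) − F(a)]/(b − a), and the interval with the largest value decides: below 0.25 Escalate, 0.25–0.35 Stay, above 0.35 De-escalate.

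**3. Reproduce the plan's own figures.**
- The rule gives 3/6 = De-escalate, as Appendix 4 states. It also gives 2/4 De-escalate, 2/7 Stay, 2/9 Escalate and 3/10 Stay, as in the SAP Appendix 12.1 table.
- Simulated probabilities of selecting the MTD (4,000 trials per scenario, every DLT counted), with Appendix 4 values in brackets: scenario 1, 0.725 (0.73); scenario 3, 0.880 (0.876); scenario 4, 0.747 (0.749); scenario 5, 0.413 (0.398); scenario 6, 0.520 (0.516). Scenario 2 was not simulated.
- The mean of the six Appendix 4 values is (0.73 + 1 + 0.876 + 0.749 + 0.398 + 0.516)/6 = 0.7115, matching 0.712 in Table 9-2.

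**4. Compare the two tallies.** Suppose one infusion-stopping DLT occurs and one patient is added under 8.3.1. Worked examples:
- 0/3: F(p) = 1 − (1−p)^4. The mass on 0–0.05 is (1 − 0.95^4)/0.05 = 0.1855/0.05 = 3.710, the largest. Escalate.
- 1/4: F(p) = 1 − (1−p)^5 − 5p(1−p)^4. The mass on 0.25–0.35 is (0.5716 − 0.3672)/0.10 = 2.044; on 0.15–0.25 it is (0.3672 − 0.1648)/0.10 = 2.024. Stay, by a narrow margin.

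| Situation at the dose | 5.4.5.1-evaluable only | All treated patients and DLTs |
|---|---|---|
| First cohort, added patient DLT-free | 0/3 Escalate (3.710) | 1/4 Stay (2.044 v 2.024) |
| First cohort, added patient has a DLT, infusion complete | 1/3 Stay (1.753 v 1.720) | 2/4 De-escalate (1.863) |
| Six evaluable, no other DLT | 0/6 Escalate | 1/7 Escalate |
| Six evaluable, one other DLT | 1/6 Escalate (2.716) | 2/7 Stay (2.507 v 2.162) |
| Nine evaluable, two other DLTs | 2/9 Escalate (2.946 v 2.640) | 3/10 Stay (2.878 v 2.344) |

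If nobody is added in the first cohort, the full count is 1/3, also Stay. The evaluable-only tally is one step less cautious in four of the five rows and the same in the other. These are table readings before any SRC judgement.

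**The case against.** The strongest reply is that 5.4.5.1 governs when a decision may be taken, not what enters the table. It never says that rows or columns are restricted to evaluable patients. Section 9.1.1, the Figure 9-1 legend and Section 5.4.6.1 all point to treated patients and all Section 5.5 DLTs. Waiting for three evaluable patients while counting every treated one is coherent, and if anything cautious: the stopped infusion may prompt one more patient while the DLT still counts, giving 1/4 = Stay. This stands. A reader might infer that the protocol directs the SRC to delete the DLT, or that its counting basis conflicts with the decision table. The documents support neither.

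The safeguards also stand. Section 5.4.5.2 makes the table an aid within a review of all relevant data. Section 5.5 has the SRC consider DLTs and review all Grade 2 or higher events before escalation. Section 3.3 pauses enrolment for Grade 4 or 5 toxicities not clearly explained by other causes. The affected group is narrow: Table 5-4 exempts Grade 3 immune-related events lasting under 7 days after corticosteroids, and SAP 8.8.4 lists infusion reactions among immune-related events, so some reactions may not be DLTs at all.

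Rewording may also come late. Amendment 07 already names Phase 2 indications, and SAP version 3.0 is dated March 2024, when the planned clinical phase (Q3 2023/Q1 2024) was due to have ended or be ending. The documents do not say that escalation is closed.

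None of this removes the difference between 5.4.5.1 and SAP 7.2.5.

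**Conclusion.** The point holds as a drafting inconsistency between protocol and SAP, at the low end of minor. Section 5.4.5.1 misclassifies a patient with a DLT on a foreseeable safety event, and SAP 7.2.5 classifies the same patient correctly. The SAP wording is probably what was intended.

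The table contrasts apply only if the SRC tallied 5.4.5.1-evaluable patients alone, which nothing in the documents prescribes. They also rest on the assumed prior and exclusion cutoff, which reproduce the plan's figures closely. The DLT incidence reported under SAP 7.2.5 is unaffected.

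A reader might go further and quote a raised chance of selecting a dose above the MTD. If 25% of DLTs stopped an infusion and every one were dropped with another patient enrolled, simulation moves that chance from 0.03 to 0.07 (scenario 1), 0.09 to 0.22 (scenario 3) and 0.07 to 0.19 (scenario 6). At 50% the figures are 0.25, 0.52 and 0.50. Both shares are assumptions absent from the documents, and systematic dropping is not a stated procedure, so these figures do not measure this trial's risk.

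A reader might also infer that the two-evaluable-patient rule permits escalation past a third patient's DLT. Section 5.4.3 confines that rule to the first cohort recruited, requires no treatment-related toxicity above Grade 1 in the two, and leaves the decision to the SRC.

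**What to change.** Reword 5.4.5.1 to match SAP 7.2.5: a patient is evaluable if they have a Cycle 1 DLT after any amount of study drug, or if they complete 21 days with full infusion of the planned doses. Add that a patient with a DLT always enters both the row and the column count of the decision table, even when an additional patient is enrolled under 8.3.1.

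If escalation is already complete, confirm from the SRC minutes that past decisions counted such patients, and record the result.

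The cost is one or two sentences and a check of existing minutes. It needs no new data and no added patients.

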# 5.4.5.2 Data for Dose Escalation Decisions

Decisions will be based on a synthesis of all relevant data available from all dose levels evaluated in the ongoing study, including safety information (all CTC grade Aes, ECGs and laboratory values, DLTs, all CTCAE v5>Grade 1 toxicity data) and available PK data from evaluable patients.

The SRC must reach a consensus on whether to declare the MTD, escalate the dose any further, or whether to de-escalate and/or recruit additional numbers of patients at the current dose level. The mTPI-2 decision table will be used by the SRC in addition to other data mentioned in this section to aid in the recommended escalation and de-escalation decisions (see Section 9).

Patient safety will be monitored on an ongoing basis by the SRC and the dose levels and continuation of dosing at a certain dose level will potentially be amended, depending on emerging data from earlier cohorts.

